Official Study Title:

The Clinical Effects of Kinesio Taping Versus Sham Taping on Pain, Kinesiophobia, Functional Mobility, and Disease Activity in Patients with Rheumatoid Arthritis: A Randomized Controlled Trial

ClinicalTrials.gov Identifier (NCT Number):

NCT0XXXXXXX

Document Date:

30 October 2024

Principal Investigator:

[name]

Istanbul Rumeli University, Faculty of Health Sciences, Department of Physiotherapy and Rehabilitation

The Effectiveness of Kinesiology Taping in Patients with Knee Rheumatoid Arthritis in Terms of Pain, Function and Kinesiophobia: A Randomised Controlled Trial

Background:**Background:**

Rheumatoid arthritis is a chronic inflammatory disease that leads to joint pain, reduced

functional capacity, and movement-related fear. Non-pharmacological and supportive treatment methods are increasingly emphasized to improve patients' quality of life. Kinesio taping has been suggested as a potential complementary approach, but its clinical benefits compared to sham applications remain uncertain.

Objective:

The aim of this study is to investigate the effects of kinesio taping compared to sham taping in patients with rheumatoid arthritis, with a particular focus on pain, functional mobility, kinesiophobia, and disease activity.

Methods:

A randomized controlled design is planned, including 30 patients with rheumatoid arthritis aged 45–65 years with moderate disease activity (DAS28: 2.6–5.1). Participants will be randomly assigned to two groups: kinesio taping or sham taping. Interventions will be applied twice a week for four weeks. Outcomes will include pain (Visual Analog Scale), disease activity (DAS28), kinesiophobia (Tampa Kinesiophobia Scale), and functional mobility (Timed Up-and-Go Test). Measurements will be taken before and after the intervention period.

Ethical Approach: All procedures conform to the ethical standards of the Helsinki Declaration and were approved by the Istanbul Rumeli University Ethics Committee.

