The Statistical analysis: The statistical evaluation of the study data will be carried out using IBM SPSS Statistics version 26.0. The distribution of quantitative variables will be examined with the Kolmogorov-Smirnov test to determine normality. Between-group comparisons of categorical variables will be performed with the Chi-square test, while continuous variables will be analyzed using the Independent Samples t-test. Pre- and post-intervention differences within each group will be assessed by the paired t-test. Statistical significance will be set at $p < 0.05$. In addition, effect sizes will be estimated as r values, calculated from the formula t / \sqrt{n} , in accordance with Cohen's d interpretation.

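### The planned effect size, t/√n, is not r, and for the kinesio versus sham comparison it understates Cohen's d

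*Combined protocol and SAP*

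**What the plan says.** The Statistical analysis paragraph plans two kinds of t-test. Between groups, "continuous variables will be analyzed using the Independent Samples t-test". Within groups, "Pre- and post-intervention differences within each group will be assessed by the paired t-test". A single effect-size rule then follows for both: "effect sizes will be estimated as r values, calculated from the formula" t/√n, "in accordance with Cohen's d interpretation". The text does not say whether n is the whole trial, one group or the number of pairs, or which t enters the formula. No other effect size is planned.

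On sample size, the Methods paragraph gives a total, "including 30 patients with rheumatoid arthritis", and states that "Participants will be randomly assigned to two groups". It gives no allocation ratio or group sizes.

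**The concern.** The sentence mixes three things that do not belong together: the name r, the formula t/√n, and the d scale for interpretation. r and d are different measures with different ranges and benchmarks, so a value cannot be labelled as one and read as the other. Because n and the source of t are open, the reported number could also differ by a fixed factor depending on a choice made after the data are seen.

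The objective of the trial is the comparison of kinesio with sham taping, and that is the contrast for which the formula fails as a d. If the rule is applied there, the standardised effect and its verbal label come out too small. If it is applied to both tests, within-group changes and the randomised contrast appear under one name but on different scales, which makes within-group change look larger relative to the contrast.

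**Working it through.** The plan prints no numerical effect size, so there is no figure to reproduce. The check compares the stated formula with the standard identities.

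**Inputs**
- Formula t/√n, label r, d interpretation, independent-samples and paired t-tests: Statistical analysis paragraph.
- N = 30 in two groups: Methods paragraph.
- Assumed, because not stated: a 15:15 split (others are shown), all 30 patients analysed, two-sided p-values, and the usual d benchmarks 0.2/0.5/0.8.

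**Step 1: is it r?** r = √(t²/(t² + df)) is always below 1, whereas t/√n grows without limit.
- Between groups, df = 28: t/√n passes 1 when t > √30 = 5.477 (n = 30) or t > √15 = 3.873 (n = 15).
- Paired, 15 pairs, df = 14: t = 3.873 (p = 0.0017) gives t/√15 = 1.00, while r = √(15/(15 + 14)) = 0.72.

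So it is not r for either test.

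**Step 2: is it d for the independent-samples t?** d = t·√(1/n1 + 1/n2) = t·√(N/(n1·n2)).
- With n = N: (t/√N)/d = √(n1·n2)/N. This is at most 1/2, because n1·n2 ≤ N²/4.
- With n = one group: (t/√n1)/d = √(n2/N), which is always below 1.

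Fraction of d that would be reported:

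| Split | n = 30 | n = smaller group | n = larger group |
|---|---|---|---|
| 15:15 | 0.500 | 0.707 | 0.707 |
| 12:18 | 0.490 | 0.775 | 0.632 |
| 10:20 | 0.471 | 0.816 | 0.577 |

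The value therefore understates d for every split and under either reading of n.

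**Step 3: size at 15:15.** Here √(2/15) = 0.365, so d = 0.365·t.
- Observed d = 0.80: t = 0.80/0.365 = 2.191, p = 0.037. Reported value 2.191/√30 = 0.40 or 2.191/√15 = 0.57; the correct r is 0.38.
- To reach 0.5 (medium), the observed d must be 0.5/0.500 = 1.00 (n = 30) or 0.5/0.707 = 0.71 (n = 15).
- To reach 0.8 (large), it must be 0.8/0.500 = 1.60 or 0.8/0.707 = 1.13.
- A value above 1 needs an observed d above 2.0 (n = 30) or 1.41 (n = 15).

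**Step 4: the paired t.** With n = number of pairs, t/√n is the mean change divided by the SD of the changes, which is d_z. The arithmetic is right here, and only the label r is wrong.

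**Step 5: one formula for both tests.** A reported 0.50 within a group of 15 is d_z = 0.50 (t = 1.936, p = 0.073). Between groups, a reported 0.50 is an observed d of 1.00 (t = 2.739, p = 0.011) if n = 30, or 0.71 (t = 1.936, p = 0.063) if n = 15.

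A check on simulated data with 15 per group confirmed the identities. At t = 3.667, the directly computed d and r (1.339 and 0.570) matched the formulas, against t/√30 = 0.669 and t/√15 = 0.947. In the paired analysis, t/√15 equalled d_z (1.044).

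**The case against.** The strongest reply is that the plan never says the formula is for the independent-samples t. The paired t-test is the last test named before the effect-size sentence, and with n as the number of pairs t/√n is exactly d_z, which sits naturally on a d-type scale. This stands as a limit: the understatement of d follows only if the formula is applied between groups. Sentence order does not settle which test is meant, and even on this reading the label r is wrong and the randomised comparison is left without any effect size.

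Second, with n = 30 and a modest t the value is numerically close to r: at t = 2.048 (the two-sided 0.05 threshold, df 28) it is 0.374 against 0.361. This is true, but the plan prescribes d interpretation, so a number near r would be judged on the wrong benchmarks; d at that t is 0.748.

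Third, the contrast between identical reported values depends on n. It is wide with n = 30 between groups (d = 1.00 against d_z = 0.50) and narrower with n = 15 (0.71 against 0.50). That is correct. The scales still differ, but the wider figure should not be quoted alone.

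Finally, the effect size is supplementary and feeds no decision rule, and a reader given t and the group sizes could recover d. That bears on severity. It does not make the sentence right.

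**Conclusion.** The concern holds. Every reading of the sentence leaves the label, the formula or the interpretation scale wrong, so this is an error in the plan and not just a missing detail. That t/√n is not r, and that it is below d for the between-group test, are algebraic facts that need no assumption about allocation. The sizes (0.50 or 0.71 of d, and an observed d of 0.80 printed as 0.40 or 0.57) rest on 15:15 with all patients analysed. The shifts in verbal label also rest on the 0.2/0.5/0.8 benchmarks, and the p-values on two-sided tests.

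Mean differences, t statistics, p-values and significance decisions are unaffected. The sentence should be corrected before results are reported, but it does not threaten the main inference.

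**What to change.** Replace the effect-size sentence with one that names the measure and defines n for each test:

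- **Between groups:** d = t·√(1/n1 + 1/n2), that is, the mean difference over the pooled SD, with n1 and n2 the numbers analysed, read on the d scale. It is best reported beside the mean difference and its 95% CI, although the CI is good practice and not needed to cure the error. If r is preferred, use r = √(t²/(t² + df)) and read it on r benchmarks.
- **Within groups:** t/√(number of pairs), labelled d_z and not r, with a note that it is not comparable with the between-group d.

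State the benchmarks used for each measure. The cost is a sentence or two of SAP wording, with no new data.
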